### **Week 16 Daily Diary Window Construction**

The following sequential steps will be used to determine the Week 16 diary window. The general goal is to anchor on the scheduled Week 16 visit (or a proximal unscheduled visit) if such a visit exists or to use an interval based on days in study for cases where a scheduled Week 16 or a proximal surrogate does not exist.

Step 1: If the Week 16 scheduled visit exists, the Week 16 diary interval is the 7 days prior to the Week 16 date provided that window has at least 4 non-missing observations. If there are less than 4 non-missing observations, the diary window's lower bound will be extended 1 day at a time (up to day 99) to a maximum of 14 days prior to the Week 16 date until 4 non-missing observations are obtained. If, after extending this diary window's lower bound to 14 days, there are less than 4 non-missing observations then go to Step 2.

Step 2: If the Week 16 scheduled visit does not exist, the 7 days prior to the last visit (scheduled or unscheduled) occurring after Day 105, will constitute the Week 16 diary window provided that window contains at least 4 non-missing observations. If there are less than 4 non-missing observations, the diary window's lower bound will be extended 1 day at a time (up to Day 99) to a maximum of 14 days prior to the unscheduled visit date until 4 non-missing observations are obtained. If, after extending this diary window's lower bound to 14 days, there are less than 4 non-missing observations then go to Step 3.

Step 3: If neither a Week 16 scheduled visit is available nor an unscheduled visit to act as a surrogate for the Week 16 diary window, then the Week 16 window will be Day 106 to Day 112. If there are less than 4 non-missing observations, the diary window's lower bound will be extended 1 day at a time to Day 99 until 4 non-missing observations are obtained.

If the steps above do not detect a window with at least 4 non-missing observations, then the Week 16 window is 7 days from either the Week 16 visit, the surrogate visit or Days 106 through 112 and the mean is missing and subject to imputation rules.

### **Week 15 Daily Diary Window Construction**

The lower boundary of the Week 15 diary window is defined as Day 99. The upper bound of the Week 15 diary window is the minimum of either Day 105 or the lower bound of the Week 16

diary window -1. Consequently, Week 15 may be less than 4 days if the Week 16 scheduled visit is before Day 112. Moreover, as Week 15 diary window cannot exceed 7 days, there could be daily assessments between Weeks 15 and 16 diary windows that do not fall into a diary window. If after constructing the diary windows, there are fewer than 4 non-missing values the mean for Week 15 is missing and subject to imputation rules.

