Treatment comparisons of discrete efficacy variables will be made using a logistic regression analysis with treatment, baseline disease severity, and region in the model. The proportions and 95% confidence interval (CI) will be reported. If a patient needs to use rescue medication, the data after rescue onward will be considered missing and missing data will be imputed using the nonresponder imputation (NRI) method. All patients who discontinue the study or study treatment at any time for any reason will be defined as nonresponders for the NRI analysis for categorical variables after discontinuation onward. Additional analyses will be done using all observed data whether rescue medication was used or not.

Treatment comparisons of continuous efficacy and health outcome variables will be made using mixed-effects model of repeated measures (MMRM) with treatment, region, baseline severity, visit, and treatment-by-visit interaction as fixed categorical effects and baseline score and baseline score-by-visit interaction as fixed continuous effects. An unstructured covariance matrix will be used to model the within-patient variance-covariance errors. Type III sums of squares for the least squares means (LSMs) will be used for the statistical comparison and contrasts will be set up within the model to compare treatment groups at specific time points of interest.

Fisher exact test will be used for all adverse events (AEs), baseline, discontinuation, and other categorical safety data. Continuous vital signs and laboratory values will be analyzed by an analysis of covariance (ANCOVA) with treatment and baseline values in the model.

2. Schedule of Activities

Table JAIY.1. I4V-MC-JAIY Schedule of Activities

	Screening	Double-Blind, Placebo-Controlled							Post-treatment Follow-up
	Period 1	Period 2							Period 3
Visit Number	1	2	3	4	5	6	7	8	801 ^a
Weeks from Randomization		0	1	2	4	8	12	16 or ET	
Days from Randomization		0	7	14	28	56	84	112	
Visit Tolerance Interval (days)	-8 to -35		±2	±2	±2	±4	±4	±4	28 ± 4 after last dose
Procedure									
Inclusion and exclusion review	X	X							
Informed consent	X								
Clinical Assessments									
Demographics	X								
Medical history	X								
Substance Use (alcohol, tobacco use)	X								
Previous and current AD treatments	X								
Weight	X	X			X	X	X	X	X
Height		X							
Vital signs (BP and pulse rate)	X	X	X	X	X	X	X	X	X
Physical examination	X								
Symptom-directed physical examination ^b		X	X	X	X	X	X	X	X

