5.1.2. Period 2: Double-Blind, Placebo-Controlled Treatment

At Visit 2 (Week 0, baseline), study eligibility for each patient will be reviewed, based on all inclusion and exclusion criteria (Section 6), and laboratory test results. Patients who meet all criteria will proceed to randomization and begin the 16-week double-blind, placebo-controlled treatment period.

At Visit 2, after laboratory samples are collected and all assessments are completed, patients will take the first dose of investigational product at the clinic.

Patient will be randomized at a 1:1:1 ratio into 1 of the 3 treatment groups (placebo QD, baricitinib 2-mg QD, or baricitinib 4-mg QD). Investigational product will be administered daily for 16 weeks (treatment period Visits 2 through 8; Section 7). All patients will be required to use emollients daily. Daily diaries will continue to be utilized throughout the treatment period. Download of this data will be required at study visits. TCS will be dispensed at V2 and used on affected areas as described in section 7.7.2. Topical calcineurin inhibitors (TCNIs) is also allowed, but TCNI use should be limited to problem areas (e.g. face and skin folds). The use of higher potency TCS and systemic therapies for the treatment of AD are not allowed, except as part of rescue therapy for patients not responding to treatment. Details of background topical therapy, as well as rescue therapy and rescue criteria are included in Section 7.7. Assessments of disease severity will be performed by the investigator at all study visits including unscheduled and early termination visits (ETVs).

The primary efficacy endpoint and final visit in the treatment period will be at Week 16 (Visit 8). Patients who complete through the Week 16 study visit may be eligible for inclusion in the long-term extension study JAHN (up to 2 additional years of treatment).

If a patient discontinues investigational product for any reason, the patient should remain in the study through Week 16 (Visit 8). If the patient refuses and wishes to withdraw consent, an ETV should be performed as soon as logistically possible.

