### **6.2.2. Definition of Baseline and Postbaseline Measures**

The baseline value for efficacy and health outcomes variables measured at scheduled visits is defined as the last non-missing measurement on or prior to the date of first study drug administration (expected at Week 0, Visit 2).

The baseline value for the daily diary assessments (Itch NRS, ADSS, Skin Pain NRS, PGI-S-AD) is the mean of the non-missing assessments in the 7 days prior to the date of first study drug administration (expected at Week 0, Visit 2).

If there are less than 4 non-missing assessments in the baseline diary window, the interval lower bound can be extended up to 7 additional days, one day at a time, to obtain the most recent 4 non-missing values. If there are not at least 4 non-missing assessments in the baseline period, the baseline mean is missing.

Baseline for the safety analyses is defined as the last non-missing scheduled (planned) measurement on or prior to the date of first study drug administration for continuous measures by-visit analyses and all non-missing measurements on or prior to the date of first study drug administration for all other analyses.

Postbaseline measurements are collected after study drug administration through Week 16 (Visit 8) or early discontinuation visit. Efficacy data collected at scheduled visits (e.g., eCOA, ClinRO) will be used in all analyses unless it is missing. If an assessment is missing at a scheduled visit, an unscheduled post-baseline assessment can be used provided it falls within the

window interval as follows: a  $\pm 2$  day window is used for Visit 3 (Week 1), Visit 4 (Week 2), and Visit 5 (Week 4); and a  $\pm 4$  day window is used to Visit 6 (Week 8), Visit 7 (Week 12), and Visit 8 (Week 16). If there is more than 1 unscheduled visit within the defined visit window and no scheduled visit assessment is available, the unscheduled visit closest to the scheduled visit date will be used. If two unscheduled visits of equal distance are available, then the latter of the two will be used.

Postbaseline daily diary endpoints will be the mean of weekly visit windows (diary windows) anchored on day of first dose (Day 1) for Weeks 1 through 14 as follows: Week 1 (Days 1 through 7), Week 2 (Days 8 through 14), Week 3 (Days 15 through 21), ..., Week 14 (Days 92 through 98).

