### **6.4.1. Nonresponder Imputation**

A nonresponder imputation (NRI) method imputes missing values as non-responses and can be justified based on the composite strategy for handling intercurrent events (ICH E9 R1). This imputation procedure assumes the effects of treatments disappear after the occurrence of an intercurrent event defined by the associated censoring rule.

All categorical endpoints will utilize the NRI method after applying the primary censoring rule to patients who permanently discontinued study drug or were rescued (described in Section 6.4). Additionally, all primary and key secondary categorical endpoints will utilize NRI after applying the secondary censoring rule as sensitivity analyses. For analyses which utilize either of the censoring methods, randomized patients without at least 1 post-baseline observation will be defined as nonresponders for all visits.

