	Proportion of patients achieving a 4- point improvement in Skin Pain NRS in subgroup of patients with baseline Skin Pain NRS $\geq 4$	Logistic regression using NRI	ITT	Bari 4 mg or Bari 2 mg vs PBO; Week 1,..., 16	Other Secondary Analysis
Atopic Dermatitis Sleep Scale (ADSS)	
 
ADSS item scores
 
Change from baseline in ADSS item scores
 
	MMRM	ITT	Bari 4 mg or Bari 2 mg vs PBO; Week 1,..., 16	Key Secondary Analysis at Week 1 and 16
			PPS	Bari 4 mg or Bari 2 mg vs PBO; Week 16	Sensitivity analysis
		ANCOVA using mLOCF	ITT	Bari 4 mg or Bari 2 mg vs PBO; Week 1,..., 16	Sensitivity Analysis
		pMI	ITT	Bari 4 mg or Bari 2 mg vs PBO; Week 16	Sensitivity analysis
Patient-Oriented Eczema Measure (POEM)	
 
POEM score
 
Change from baseline in POEM score
 
	MMRM	ITT	Bari 4 mg or Bari 2 mg vs PBO; at each post-baseline visit	Secondary Analysis
			ANCOVA using mLOCF	ITT	Bari 4 mg or Bari 2 mg vs PBO; Week 16
	Proportion of patients achieving a 4- point improvement in subgroup of patients with baseline POEM $\geq 4$	Logistic regression using NRI	ITT	Bari 4 mg or Bari 2 mg vs PBO; at each post-baseline visit	Secondary Analysis
Patient Global Impression of Severity–Atopic Dermatitis (PGI-S- AD)	
 
PGI-S-AD score
 
Change from baseline in PGI-S-AD score
 
	MMRM	ITT	Bari 4 mg or Bari 2 mg vs PBO; at each post-baseline visit	Secondary Analysis
			ANCOVA using mLOCF	ITT	Bari 4 mg or Bari 2 mg vs PBO; Week 16

Measure	Variable	Analysis Method (Section 6.2.3)	Population (Section 6.2.1)	Comparison/Time Point	Analysis Type
Hospital Anxiety Depression Scale (HADS)	
 
HADS domain scores
 
Change from baseline in HADS domain
 
	MMRM	ITT	Bari 4 mg or Bari 2 mg vs PBO; Week 2, 4, 8, 16	Secondary Analysis
		ANCOVA using mLOCF	ITT	Bari 4 mg or Bari 2 mg vs PBO; Week 16	Sensitivity Analysis
Dermatology Life Quality Index (DLQI)	
 
DLQI total score
 
Change from baseline in DLQI
 
Observed and change from baseline in domain scores 
 
-Symptoms and feelings
 
-Daily activities
 
-Leisure
 
-Work and school
 
-Personal relationships
 
-Treatment
 
 
 
	MMRM	ITT	Bari 4 mg or Bari 2 mg vs PBO; Week 16	Secondary Analysis

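### An early but in-window Visit 8 shortens the Week 15 diary window to 3 to 6 days while the 4-entry minimum stays, so nonresponder imputation lowers Week 15 itch and skin pain response rates

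*SAP*

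**What the plan says.** SAP Section 6.2.2 builds weekly diary windows "anchored on day of first dose (Day 1) for Weeks 1 through 14". Week 16 is normally the 7 days before the scheduled Week 16 visit. Week 15 starts at a fixed Day 99 and stops at Day 105 or the day before the Week 16 window, whichever is earlier. The SAP recognises the effect: "Consequently, Week 15 may be less than 4 days if the Week 16 scheduled visit is before Day 112". It nevertheless keeps the usual minimum: if "there are fewer than 4 non-missing values the mean for Week 15 is missing and subject to imputation rules". Week 15 has no extension rule, whereas the baseline and Week 16 windows can be lengthened to find 4 entries.

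For binary endpoints the imputation rule is nonresponder imputation (NRI), which "imputes missing values as non-responses" (SAP Section 6.4.1). SAP Section 6.4 lists an intermediate missed visit among the intercurrent events, and Section 6.4.1 applies NRI to all categorical endpoints. Table JAIY.6.7 plans NRI logistic regression for the 4-point Itch NRS response at Day 2 and Weeks 1 to 16. It plans the same for the 4-point Skin Pain NRS response, "Bari 4 mg or Bari 2 mg vs PBO; Week 1,..., 16". Both rows include Week 15.

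**The concern.** SAP Section 6.4.1 justifies NRI by assuming that the treatment effect is gone after an intercurrent event. Attending Visit 8 early but within tolerance is not such an event. The diary entries exist; the later ones have only been assigned to Week 16. Under the stated rule, some patients are scored as Week 15 failures because of when they were seen, and others because the shortened window leaves little or no room for a missed entry.

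At stake is the by-week response curve. Week 15 can show a dip that neighbouring Week 14 (always 7 days) and Week 16 (extendable) do not have. Because it sits next to the Week 16 result, it could be read as unstable response.

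**Working it through.** **Visit 8 in SAP days.** The protocol's Table JAIY.1 puts Visit 8 at 112 on the row "Days from Randomization", with a tolerance of ±4. At Visit 2, the randomization visit, "patients will take the first dose of investigational product at the clinic" (Protocol Section 5.1.2), so randomization day 0 is SAP Day 1. In-window visits therefore run from 112 − 4 + 1 = Day 109 to 112 + 4 + 1 = Day 117, with nominal Day 113. Step 3 of the Week 16 rule agrees: its default window, Days 106 to 112, is the 7 days before Day 113.

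**Window length.** For a visit on Day v, Week 16 is Days v − 7 to v − 1. Week 15 length = min(105, v − 8) − 98.

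The chance that the mean is missing is P(X ≤ 3), with X binomial(length, c) and c the assumed daily diary completion:

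| Visit 8 day | Week 15 days | c = 100% | c = 90% | c = 85% |
|---|---|---|---|---|
| 109 | 3 | 100% | 100% | 100% |
| 110 | 4 | 0% | 34.4% | 47.8% |
| 111 | 5 | 0% | 8.1% | 16.5% |
| 112 | 6 | 0% | 1.6% | 4.7% |
| 113–117 | 7 | 0% | 0.3% | 1.2% |

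This reproduces the SAP's remark that Week 15 can be shorter than 4 days. By this arithmetic that happens for visits before Day 110; visits on Days 110 and 111 shorten the window but leave at least 4 days.

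**Reading of the text.** If the visit date counted among the 7 days, a Day 109 visit would leave 4 days. If 112 were read as a SAP day, the earliest in-window visit would be Day 108 and would leave 2. The reading used here fits Step 3.

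**Averaging over visit days.** The documents give no distribution of visit days, so four assumed ones over Days 109 to 117 are shown. Triangular weights are 1, 2, 3, 4, 5, 4, 3, 2, 1 over 25. The normal cases are centred on Day 113 and truncated to the window.

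| Visit timing (assumed) | Share seen on Day 109 | Missing, c = 90% | Missing, c = 85% |
|---|---|---|---|
| Normal, SD 1 day | below 0.1% | 1.2% | 3.1% |
| Normal, SD 1.5 days | 0.8% | 3.4% | 6.1% |
| Triangular | 4.0% | 8.1% | 11.3% |
| Uniform | 11.1% | 16.2% | 19.5% |
| Full 7-day week, for comparison | – | 0.3% | 1.2% |

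Worked example, uniform at 90%: (1 + 0.344 + 0.081 + 0.016 + 5 × 0.003) / 9 = 1.456 / 9 = 0.162.

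**Effect on reported rates.** If timing and completion are unrelated to response, reported rate = true rate × (1 − missing share). For an illustrative true 40% against 20% (difference 20 points):

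- SD 1 day, 90%: 40 × 0.988 = 39.5 against 19.8; difference 19.8 (unrounded rates)
- Triangular, 90%: 40 × 0.919 = 36.7 against 18.4; difference 18.4
- Uniform, 85%: 40 × 0.805 = 32.2 against 16.1; difference 16.1

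With perfect diaries only the Day 109 patients are lost. At 40% response the dip is then 0.04 × 40 = 1.6 points (triangular) or 0.111 × 40 = 4.4 points (uniform).

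**The case against.** The SAP foresaw the short window and stated it. Anchoring Week 16 on the actual visit is sensible, because Week 16 carries the key diary endpoints and Week 15 has no scheduled visit. The entries taken from Week 15 are used in Week 16. Visit timing applies to all arms under blinding, and the effect pulls the difference toward zero, so it cannot create a false claim of benefit. All of this stands. It limits the consequence, but it does not explain why a patient with a complete diary should be scored a nonresponder.

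Three stronger readings are tempting and are not supported.

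- A reader might infer that fully compliant patients fail whenever they are seen a few days early. With a complete diary this happens only on Day 109, one day of nine. On Days 110 to 112 a patient must also have missed entries. In the triangular case at 85% completion, Day 109 accounts for 4.0 of the 11.3 points.
- A reader might take missingness of 8 to 20% as the expected size. That range needs visits spread widely over the window; tighter timing gives 1 to 6%.
- A reader might infer from the Other Secondary label in Table JAIY.6.7 that Week 15 skin pain response is a stated objective. SAP Section 4.2.2 names that endpoint at 16 weeks only and lists it among objectives not adjusted for multiplicity.

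**Conclusion.** The point holds as a minor defect in a stated rule. With Visit 8 on Day 109 a Week 15 mean is impossible, and on Days 110 to 112 it is harder to obtain. NRI turns the resulting missing values into failures in the planned Week 15 itch and skin pain responder analyses. The direction is certain if any such patient would have responded: rates fall in all arms, by more in absolute terms where response is higher.

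The size is not known. It rests on assumed visit timing and diary completion, independent daily entries, and no link between either and response. At 85 to 90% completion the missing share runs from about 1% to 19.5%, against 0.3 to 1.2% for a full week.

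Confirmatory inference is not affected. The key secondary diary hypotheses in SAP Section 6.6 are at Day 2 and Weeks 1, 2, 4 and 16, and the Week 16 derivation is unchanged. Continuous diary endpoints use MMRM: they may lose one repeated measure, but nobody is scored as a failure.

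**What to change.** In SAP Section 6.2.2, define the Week 15 window as Days 99 to 105 for every patient and allow it to overlap the Week 16 window. Keep the 4-entry minimum, and keep NRI for genuine diary non-completion, rescue and discontinuation. This takes one or two sentences and a small change to the diary derivation, made before unblinding.

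The cost is that some days count toward both means when Visit 8 is early: Days 102 to 105 (4 days) for a Day 109 visit, then 3, 2 and 1 days for Days 110, 111 and 112. The overlap is larger when sparse entries push the Week 16 window back toward Day 99.

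If overlap is not wanted, keep the current window and the 4-entry minimum, but treat Week 15 as not assessed, and outside the NRI denominator, only when Visit 8 timing leaves fewer than 4 days. The cost is a slightly smaller Week 15 denominator. This version does not restore the lost tolerance for missed entries on Days 110 to 112. Lowering the 4-entry minimum instead is not advised: it would accept 2-entry means from a short window, which the SAP accepts in no other week.

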### **Handling of Duplicate Diary Records**

If there is more than one diary record on a particular date, the first record on that particular date will be used in the analysis.

Note, as some analyses require use of the primary censoring rule, assessments collected on the day of rescue or afterwards will be excluded from the weekly visit interval calculation when implementing the rule for daily diary. If, after exclusion of these records, there are less than 4 non-missing assessments, the weekly interval which implements the primary censoring rule will be missing. The post-study follow-up weekly score for daily diaries will be calculated as the mean of the 7 days prior to the follow-up visit which occur after last dose of study treatment.

Postbaseline measures for the safety analyses are defined as the non-missing scheduled (planned) measurements after the date of first study drug administration for continuous measures by-visit analyses and all non-missing measurements after the date of first study drug administration for all other analyses.

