Treatment comparisons for continuous efficacy and health outcomes variables may also be made using analysis of covariance (ANCOVA) for primary and key secondary objectives. When an ANCOVA model is used, the model includes region, baseline disease severity, treatment group, and baseline value. Treatment LSM will be estimated within the framework of the ANCOVA using type 3 sums of squares. Reported differences in LSM and associated p-values, standard errors and 95% CI will be used for statistical inference. Treatment-by-region interaction will also be added to the model for sensitivity purposes and is discussed in Section 6.5.

Beginning on Day 14 a Cox proportional hazard (CPH) model of time (in days) to first observance of a 4-point itch reduction with effects for treatment, region, baseline mean itch, and disease severity will be used to test for treatment differences from placebo. For this analysis, daily itch scores will be compared to the baseline to determine if a 4-point itch reduction has been achieved in patients with a baseline itch of at least 4. The baseline for Itch NRS is defined in Section 6.2.2. Beginning on Day 14, the day on which the first time itch NRS is reduced by at least 4 will be modeled. If any significant difference between any baricitinib dose and placebo is observed then the same analyses will be run on Day 13. This process of evaluating at the next lowest day will proceed until no significant differences are observed. No adjustments for multiple tests and multiple comparisons will be used. This analysis uses the Primary Censoring Rule for patients who are rescued or permanently discontinue study drug (see Section 6.4). Missing daily itch data will be replaced using NRI rule which means missing data is replaced with a non-response which would entail replacing missing values with a time to event of >14 days, censored; >13 days, censored, etc., depending on the window being used. If the model assumptions for the CPH model do not hold, a log-rank test will be used.

Restricted mean survival time will be evaluated at Days 2, 3, 4 and 5 as an exploratory analysis. The model will include terms for baseline disease severity (IGA), baseline itch, region, and treatment group.

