### 6.4. Handling of Dropouts or Missing Data

Intercurrent events (ICH E9 R1) are events which occur after the treatment initiation and make it impossible to measure a variable or influence how it would be interpreted.

Depending on the estimand being addressed, different methods will be used to handle missing data as a result of intercurrent events. Intercurrent events can occur through the following:

- application of one of the censoring rules (including after permanent study drug discontinuation or after rescue therapy)
- discontinuation

- missing an intermediate visit prior to discontinuation or rescue
- lost to follow-up.

Non-censor intercurrent events are events that are not due to the application of any censoring rule, i.e., the last 3 items in the list above.

Note that as efficacy and health outcome data can accrue after a patient permanently discontinues study drug or begins rescue therapy, specific general censoring rules to the data will be applied to all efficacy and health outcome observations subsequent to these events depending on the estimand being addressed. These specific censoring rules are described below.

The *primary censoring rule* will censor efficacy and health outcome data after permanent study drug discontinuation or after rescue therapy. This censoring rule will be applied to all continuous and categorical efficacy and health outcome endpoints. This censoring rule is equivalent to using all the data up to rescue.

A *secondary censoring rule* will only censor efficacy and health outcome data after permanent study drug discontinuation. This sensitivity analysis will include all observed values up to study drug discontinuation. The secondary censoring rule will be applied to primary and key secondary efficacy and health outcome endpoints as sensitivity analyses.

Table JAIY.6.1 describes the planned imputation methods for efficacy and health outcome endpoints with associated censoring rules. Sections 6.4.1 through 6.4.5 summarize the methodology of each imputation rule.

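### Two SAP sentences drop permanent drug discontinuation from the primary censoring rule; coded literally, the weekly-diary instruction would keep off-drug records in 7 of 12 key secondary tests per dose

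*SAP*

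**What the plan says.** **The definition.** SAP 6.4 says that the primary censoring rule "will censor efficacy and health outcome data after permanent study drug discontinuation or after rescue therapy". Its scope is complete: "This censoring rule will be applied to all continuous and categorical efficacy and health outcome endpoints". The secondary rule, used for sensitivity analyses, "will only censor efficacy and health outcome data after permanent study drug discontinuation".

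**Text that agrees with the definition.**
- SAP 6.4.1: "All categorical endpoints will utilize the NRI method after applying the primary censoring rule to patients who permanently discontinued study drug or were rescued".
- SAP 6.2.3, on time to itch response (a daily-diary analysis): "This analysis uses the Primary Censoring Rule for patients who are rescued or permanently discontinue study drug".
- SAP 6.11.1, on background TCS, applies the rule at rescue or stopping drug, whichever comes first.
- SAP 6.12.1 and 6.12.2 state the assumption behind the primary and secondary analyses: response is lost after rescue or permanent discontinuation.
- Protocol 10.3.1 makes patients who stop study treatment nonresponders for categorical variables and sets continuous data to missing after rescue or discontinuation.

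**Text that does not.**
- SAP 6.4, directly after the scope sentence: "This censoring rule is equivalent to using all the data up to rescue".
- SAP 6.2.2, under the subheading on duplicate diary records, explains how to apply the primary rule to daily diaries: "assessments collected on the day of rescue or afterwards will be excluded from the weekly visit interval calculation". Discontinuation is not mentioned.

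**Whether off-drug records will exist.** Protocol 5.1.2 asks patients who stop investigational product to remain in the study to Week 16 and keeps the daily diary running throughout the treatment period. Protocol 8.1.2 repeats the encouragement to stay.

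**The concern.** The two sentences leave out the same event. One is a gloss on the definition. The other is the instruction a programmer would code from, because no other text says which diary records to remove before a weekly mean is taken.

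Take a patient who stops drug, is never rescued and keeps filling in the diary. Under the definition, records after the stop are missing and go to nonresponder imputation or MMRM. Under 6.2.2 taken literally, they enter the weekly mean. The same patient could be a Week 16 itch responder in one dataset and a nonresponder in the other.

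The tests concerned lie in the family controlled at a two-sided 0.05 (SAP 6.6). If the discrepancy were noticed only after unblinding, resolving it would be a post-hoc choice on confirmatory tests.

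**Working it through.** **1. The plan's own figure.** The documents give no number for this issue. The one design figure is 89% power for IGA 0/1, with 100 per arm, 10% versus 30%, two-sided alpha 0.025 and Fisher's exact test. Exact enumeration over the two binomials gives 0.891, which agrees. Nothing below changes it.

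**2. Which patients are treated differently.**
- Rescued, still on drug: both texts exclude from rescue. They agree, apart from the rescue day itself (step 6).
- Rescued with systemic therapy: Protocol 7.7.4 requires drug to be stopped, and rescue already triggers exclusion. They agree.
- Stops drug, never rescued: the definition excludes after the stop; 6.2.2 keeps everything. They differ.
- Stops drug, rescued later: the texts differ for the days between the two events.

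So the gap concerns off-drug time that is not preceded by rescue.

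**3. Which tests are reached.** SAP 6.6 lists 12 key secondary hypotheses per dose: EASI75, EASI90, EASI percent change, SCORAD75, Itch NRS at Day 2 and Weeks 1, 2, 4 and 16, Skin Pain at Week 16, and ADSS Item 2 at Weeks 1 and 16.
- Built on daily-diary measures (SAP 6.2.2): Itch 5 + Skin Pain 1 + ADSS 2 = 8.
- Built on weekly means, which is what the 6.2.2 instruction governs: 8 − 1 = 7, because Day 2 itch is a single day.
- Over both doses: 7 × 2 = 14 of 24.

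Day 2 itch is touched only by the equivalence sentence. Read literally, that sentence covers every endpoint, including the primary.

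**4. Where exposure is likely.** To matter at Week 1 or 2, a patient must permanently stop drug within days, go unrescued and keep the diary. That will be rare, so practical exposure is mainly Itch at Weeks 4 and 16, and Skin Pain and ADSS Item 2 at Week 16. For the continuous measures, SAP 6.2.3 puts all weekly diary assessments into the MMRM, so retained off-drug weeks before Week 16 would enter the model too.

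**5. Size, on assumed inputs.** The documents give no discontinuation rate. Let d be the share of an arm that stops drug without rescue and keeps the diary, and q the share of those who meet the 4-point itch criterion off drug. Under the definition they contribute 0 responders; under the literal text they contribute d × q.
- Assumed d = 2%, q = 10%: 0.02 × 0.10 = 0.2 points.
- Assumed d = 5%, q = 30%: 0.05 × 0.30 = 1.5 points.
- Assumed d = 10%, q = 50%: 0.10 × 0.50 = 5.0 points.

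These are shifts in one arm's rate. The shift in the treatment difference is d_B × q_B − d_P × q_P (B = baricitinib, P = placebo). It is 0 if the arms behave alike. At the assumed extremes it is 5.0 − 0.2 = +4.8 or 0.2 − 5.0 = −4.8 points, so the sign is open.

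**6. Two knock-on effects.** As defined, the secondary rule relaxes the primary one by keeping post-rescue data. If the primary rule were coded on rescue alone, it would keep records that the secondary rule censors, so the sensitivity analysis would no longer simply relax one condition. Separately, 6.2.2 excludes from the day of rescue, whereas 6.4 censors after rescue; the two differ by that day's record.

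**The case against.** The strongest reply is that the rule is not in doubt. SAP 6.4 states both events for all endpoints, and 6.2.3, 6.4.1, 6.11.1, 6.12.1, 6.12.2 and Protocol 10.3.1 follow it. For the itch responder tests, 6.4.1 on its own makes an unrescued discontinuer a nonresponder. On this view the 6.2.2 sentence is a subordinate note: it refers to the primary rule by name and adds a boundary detail for averaging. The equivalence sentence is then loose shorthand for the contrast with the secondary rule, which keeps data after rescue.

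Most of this stands. Intent is clear, and the 6.2.2 sentence is better read as an omission than as a competing rule. It does not excuse the text. The sentence presents itself as the way to implement the rule for diaries, nothing else works at record level for weekly means, and the equivalence sentence repeats the same omission inside the definition.

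A reader might infer that the diary instruction reaches all eight diary-based tests equally. It does not: Day 2 itch is not a weekly mean, and the earliest time points are barely exposed. A reader might also infer a bias in favour of baricitinib or an inflated Type I error. The documents do not support that, because both arms would shift and no rates are given.

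**Conclusion.** Wrong as written, with clear intent. The SAP's definition, its stated estimands and the protocol all censor at rescue or permanent discontinuation; one sentence in 6.2.2 and one in 6.4 do not. Literal use of 6.2.2 would admit off-drug diary records to 7 of the 12 key secondary tests per dose, chiefly at Weeks 4 and 16.

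Neither the size nor the direction of the effect on a treatment difference can be determined. The one-arm shifts of 0.2 to 5.0 points rest wholly on assumed inputs and are illustrative.

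The equivalence sentence might tempt a reader to conclude that the primary IGA analysis is itself compromised. It is not: 6.12.1 states that analysis with both events. The stated power and the control of alpha are likewise untouched.

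**What to change.** Three edits to the SAP, made before unblinding:

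1. In 6.2.2, state that under the primary rule diary assessments are excluded if they fall on or after the day of rescue, or after permanent discontinuation of study drug, whichever is earlier. Under the secondary rule, exclude only those after permanent discontinuation. The whichever-is-earlier construction is already used in 6.11.1.
2. In 6.4, delete the sentence that equates the primary rule with all data up to rescue.
3. Use one boundary in both sections, so that a record on the day of rescue is either in or out everywhere.

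The cost is a few sentences. No new data are needed, and sample size, alpha allocation and estimands stay as they are. Once both events are named, no key secondary test depends on which sentence the programmer follows.
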